To assess the safety of GSK2838232 administered as non-boosted once-daily doses of a tablet formulation for 11 days	GSK2838232 safety parameters: adverse events; absolute values and changes over time of clinical laboratory evaluations (hematology, clinical chemistry, urinalysis), vital signs, and ECG parameters from pre-dose values
To assess the pharmacokinetics of GSK2838232 administered as non-boosted once-daily doses of a tablet formulation for 11 days	 Day 1 dose: AUC(0-τ), Cmax, Cτ, tmax, tlag Day 11 dose: AUC(0-τ), AUC(0-∞), Cmax, Cτ, tmax, t½, tlast
Secondary	1
To assess time to steady-state of GSK2838232 when administered as non-boosted once-daily doses of a tablet formulation for 11 days	Pre-dose concentrations on Days 2 to 11
To assess accumulation of GSK2838232 when administered as non-boosted once-daily doses of a tablet formulation for 11 days	• Accumulation ratios: Ro[AUC(0-τ)], R(Cmax), R(Cτ)

AUC(0- τ) = Area under the curve (Area under the plasma drug concentration-time curve from pre-dose to the end of the dosing interval at steady state); AUC(0-inf)= Area under the concentration-time curve from time zero (pre-dose) extrapolated to infinite time; Cmax= Maximum observed concentration; t1/2= Apparent terminal phase half-life; tmax= Time of occurrence of Cmax; tlag= Lag-time (time delay between drug administration and first observed concentration above LOQ in plasma); AUC (0-t) = Area under the concentration-time curve from zero up to a definite time t

Overall Design

Part 1:

Part 1 is a relative bioavailability study that will further subdivide into two parts (Part 1A and Part 1B) (Table 1). In Part 1A, the safety and pharmacokinetics (PK) of a novel tablet formulation of GSK2838232 will be evaluated in open label, randomized, cross-over fashion against the capsule formulation as reference. Each actual treatment dose will be separated by a minimum 10-day washout period. Part 1A will be studied in the fed state using a normal fat (i.e., approximately 30%) meal in all participants. In Part 1B, the tablet will be administered in the fasted state to understand the impact of food on relative bioavailability.

Table 1 Treatment Groups in Part 1

Sequence	N	Part 1A		Part 1B				
		Period 1	Period 2	Period 3				
1	6	A	В	С				
2	6	В	A					

- 1. All treatments in Part 1A to be administered with RTV in a fed state, following two RTV pre-doses.
- 2. There will be a washout of at least 10 days between each Period.

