2. SCHEDULE OF ASSESSMENTS

Please see Table 2 and Table 3 below for the Schedule of assessments for study Parts 1 and 2 respectively.

Table 2 Schedule of Assessments for Part 1A and Part 1B: Single Dose RBA \pm Food

	Screening (within 30 days of	Periods 1 through 3													
Procedure	Day 1 - carried out over multiple days – except as noted in	Day -3	Day -2	Day -1	Day 1	Day 2	Day 3	Day 4	Day 5	Day 6	Day 7	7-14 days			
	footnotes)					24 h	48 h	72 h	96 h	120 h					
Admission to Unit	,	X2													
Outpatient Visit	Х											Х			
Informed Consent	Х														
Medical/medication/															
drug/alcohol history (Demographics)	X														
Full Physical Examination	Х														
Brief Physical Examination			Х				Х					Х			
Height, Weight, BMI	Х														
Inclusion/Exclusion	Х														
Vital signs ³	Х		Х	Χ	Χ	Χ	Х	Χ				Х			
12 Lead ECG ⁴	Х		Х	Χ	Χ	Χ	Х					Х			
Echocardiogram ⁵	Χ														
Drug/alcohol/cotinine screen	Χ	Х													
HbsAg, HCV, HIV tests	Χ														
Hem/Chem/Urine tests ⁶	Х		Х	Х		Х		Х				Х			
Serum FSH (as appropriate)	Х														
Troponin I ⁷	Х			Х	Χ	Χ		X							
24 h Holter Monitoring ⁸	Х														
Pregnancy test (women)	Χ	Χ										Χ			
Run-in Dosing with RTV			X	Χ											
Dosing with GSK2838232+RTV					X										
PK Sampling ⁹					X	Χ	X	Χ	Χ	X					
Adverse Event Review ¹⁰				X	Х	Χ	Х	Χ	Х	Х	Χ	Х			
Con Med Review			X	Χ	Χ	Χ	X	Χ	Χ	X	Χ	X			
Discharge from Unit ¹¹						X									
Out Patient Visit							X	Х	X	Χ	Χ				

BMI = Body Mass Index; ECG = Electrocardiogram; FSH = Follicle Stimulating; HbsAg = Hepatitis B surface Antigen; HCV = Hepatitis C Virus; HIV = Human Immunodeficiency Virus; Hem/Chem = Hematology/Clinical Chemistry; RTV = Ritonavir; PK = Pharmacokinetic(s); Con Med = Concomitant medications.

- 1. Follow-up Visit to take place after Treatment Period 2.
- 2. When participants stay in the unit across treatment periods, drug/alcohol/cotinine screen and pregnancy test (women) are not required on Day -3 for later periods.
- 3. On Day 1, Blood pressure (BP) and Heart rate (HR) will be collected at pre-dose (triplicate) and single assessments at 1, 2, 4, 6, 8, 12, 24, 48, and 72 h post-dose.
- 4. On Day 1, 12-lead ECG will be collected at pre-dose (triplicate), and single assessments at 1, 2, 4, 6, 8, 12, 24, 48 and 72 h post-dose.
- 5. Echocardiograms must be within 100 days of Day 1.
- 6. Samples for Chemistry and Hematology: Blood samples will be obtained after an 8-hour fast.

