- 4. Treatment B = GSK2838232 200 mg/r (as $2 \times 100 \text{ mg}$) tablet formulation, fed, normal fat (i.e., approximately 30%) meal.
- 5. Treatment C = GSK2838232 200 mg/r (as 2 x 100 mg) tablet, confirmed from Part 1A, fasted.

After completion of Part 1A, preliminary PK data will be analyzed, and a decision will be made based on tolerability, relative bioavailability PK criteria, as well as feasibility considerations, as to whether the tablet formulation will be used to conduct Part 1B (fasted) and Part 2.

Part 2:

Figure 2 Single Daily Dose Study Design Schematic

- Part 2 will evaluate non-RTV boosted GSK2838232, given as single daily doses for 11 days in a separate cohort of participants (N=8; 6A/2P).
- The placebo tablet supplied will not be identical to GSK2838232 and as such will be administered by site staff via an opaque card/paper tube to facilitate the single blind (i.e., the Principal Investigator [PI] and the participants themselves will be blinded as to their treatment).
- The dose chosen for Part 2 will depend upon the preliminary results of the tablet in Part 1A but is likely to be, but will not exceed, 500 mg (i.e., 5 x 100 mg tablets) QD.
- Participants will have a screening visit within 30 days prior to first dose, and a follow-up visit 7 to 14 days after the last dose. The maximum duration of study participation will be approximately 8 to 9 weeks.

Study Population:

The study population will consist of healthy male or female participants (women of child bearing potential [WOCBP] are permitted as long as the criteria for contraception are adhered to), as per inclusion/exclusion criteria (Section 6).

Note: Participants in both Part 1 and Part 2 will have a 24-h Holter screen as part of baseline evaluation. Holter monitoring may apply during the study period if needed.

Study Plan:

Because of the requirement to begin RTV pre-dosing 48 hours before each treatment dose in Parts 1A and 1B, participants will be admitted to the Clinical Unit three nights before each of the treatment periods and remain in the Unit until the last (120 h) PK time-point of each treatment period is collected. There is no such early admission requirement for Part 2 (non-boosted GSK2838232).

205820

If participants prematurely discontinue the study, additional participants may be randomized and assigned to the same treatment sequence at the discretion of the Sponsor in consultation with the Investigator.

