- Any SAE occurring as a result of a post-study pregnancy which is considered reasonably related to the study treatment by the Investigator, will be reported to GSK. While the Investigator is not obligated to actively seek this information in former study participants, he or she may learn of an SAE through spontaneous reporting.

Any female participant who becomes pregnant while participating will be withdrawn from the study.

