14.2 Appendix 2: Schedule of Activities

14.2.1 Protocol Defined Schedule of Events

Schedule of Assessments for Part 1A and Part 1B: Single Dose RBA \pm Food

	Screening (within 30 days of	in 30 days of													
Procedure	Day 1 - carried out over multiple days – except as noted in	Day -3	Day -2	Day -1	Day 1	Day 2	Day 3	Day 4	Day 5	Day 6	Day 7	7-14 days			
	footnotes)					24 h	48 h	72 h	96 h	120 h					
Admission to Unit		X2													
Outpatient Visit	Χ											X			
Informed Consent	Χ														
Medical/medication/															
drug/alcohol history	Χ														
(Demographics)															
Full Physical Examination	Х														
Brief Physical Examination			Х				X					X			
Height, Weight, BMI	Χ														
Inclusion/Exclusion	Χ														
Vital signs ³	Χ		X	X	X	X	Χ	Χ				X			
12 Lead ECG ⁴	Χ		Х	Χ	Х	Χ	Χ					Х			
Echocardiogram ⁵	Χ														
Drug/alcohol/cotinine screen	Χ	Χ													
HbsAg, HCV, HIV tests	Χ														
Hem/Chem/Urine tests ⁶	Χ		Х	Х		Х		Х				Х			
Serum FSH (as appropriate)	Χ														
Troponin I ⁷	Χ			X	Χ	Χ		X							
24 h Holter Monitoring ⁸	Χ														
Pregnancy test (women)	Χ	Χ										Χ			
Run-in Dosing with RTV			Х	Х											
Dosing with GSK2838232+RTV					X										

	Screening (within 30 days of	Periods 1	Periods 1 through 3											
Procedure	Day 1 - carried out over multiple days – except as noted in	Day -3	Day -2	Day -1	Day 1	Day 2	Day 3	Day 4	Day 5	Day 6	Day 7	7-14 days		
	footnotes)					24 h	48 h	72 h	96 h	120 h				
PK Sampling ⁹					X	Χ	Х	Χ	Χ	Χ				
Adverse Event Review ¹⁰				Х	Χ	Х	Х	Х	Х	Х	Х	Х		
Con Med Review			Х	Х	Χ	Χ	Х	Χ	Х	Χ	Χ	Χ		
Discharge from Unit ¹¹						Х								
Out Patient Visit							Х	Χ	Х	Χ	Χ			

205820

BMI = Body Mass Index; ECG = Electrocardiogram; FSH = Follicle Stimulating; HbsAg = Hepatitis B surface Antigen; HCV = Hepatitis C Virus; HIV = Human Immunodeficiency Virus; Hem/Chem = Hematology/Clinical Chemistry; RTV = Ritonavir; PK = Pharmacokinetic(s); Con Med = Concomitant medications.

- 1. Follow-up Visit to take place after Treatment Period 2.
- 2. When participants stay in the unit across treatment periods, drug/alcohol/cotinine screen and pregnancy test (women) are not required on Day -3 for later periods.
- 3. On Day 1, Blood pressure (BP) and Heart rate (HR) will be collected at pre-dose (triplicate) and single assessments at 1, 2, 4, 6, 8, 12, 24, 48, and 72 h post-dose.

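### For women who stay in the unit, Table 2 footnote 2 drops the scheduled pregnancy tests before Periods 2 and 3 of Part 1, although confinement cannot exclude a conception just before admission

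*Protocol*

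**What the plan says.** Protocol Section 2, Table 2, has a pregnancy-test row for women with entries at screening, on Day -3 under the heading covering Periods 1 to 3, and at follow-up. Footnote 2 qualifies the Day -3 entry: "When participants stay in the unit across treatment periods, drug/alcohol/cotinine screen and pregnancy test (women) are not required on Day -3 for later periods". SAP Section 14.2.1 reproduces the schedule with the same waiver: "drug/alcohol/cotinine screen and pregnancy test (women) are not required on Day -3 for later periods".

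Other passages that bear on it:

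- Section 5.1 admits women of childbearing potential, who "are permitted as long as the criteria for contraception are adhered to". Section 6.1, inclusion criterion 6, requires that a female participant not be pregnant.
- Appendix 6 (Section 12.6) states: "Any female participant who becomes pregnant while participating will be withdrawn from the study". It also requires a test after a missed cycle or when pregnancy is suspected, and allows further tests at the investigator's discretion.
- Section 5.1 describes the ordinary stay: "participants will be admitted to the Clinical Unit three nights before each of the treatment periods", and they are to "remain in the Unit until the last (120 h) PK time-point of each treatment period is collected".
- On spacing, the synopsis says: "There will be a washout of at least 10 days between each Period". It places follow-up 7 to 14 days after the last dose, whereas Table 2 footnote 1 places it after Period 2.

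**The concern.** Footnote 2 applies one argument to two kinds of test. A participant who has not left the unit has had no opportunity for new drug, alcohol or nicotine use, so a negative screen on the first admission stays informative. A pregnancy test differs because its result can change during the stay through something that happened before it. A woman who conceived in the last days before Period 1 admission may test negative on Day -3 and become detectable while resident. A woman with the same history who goes home and returns is retested at the next Day -3.

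What is at stake is exposure of an early pregnancy to GSK2838232 and ritonavir in a healthy volunteer who is offered no expected benefit. The protocol makes non-pregnancy an entry condition and a detected pregnancy a reason for withdrawal. No endpoint or estimate depends on this point.

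**Working it through.** The plan states no figure for this point, so the check is a day count on the minimum schedule.

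**Inputs**
- Day -3 to Day 1 is 3 days (no Day 0): Table 2.
- Doses are at least 10 days apart: synopsis and Section 5.1.
- Ritonavir is given on Day -2, Day -1 and Day 1 of each period: Table 2.
- Follow-up is 7 to 14 days after the last dose: synopsis and Section 5.1.

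**Days after the Period 1 Day -3 test, for a woman resident throughout**

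| Event | Earliest day |
|---|---|
| Period 1 dose | 3 |
| Period 2 Day -3 test, waived | 3 + 10 - 3 = 10 |
| Period 2 ritonavir run-in starts | 11 |
| Period 2 dose | 3 + 10 = 13 |
| Period 3 Day -3 test, waived | 13 + 10 - 3 = 20 |
| Period 3 ritonavir run-in starts | 21 |
| Period 3 dose | 13 + 10 = 23 |
| Follow-up test | 23 + 7 = 30 to 23 + 14 = 37 |

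The gap between scheduled tests is at least 30 to 37 days. Periods 2 and 3 add 2 doses of GSK2838232 200 mg and 2 x 3 = 6 doses of ritonavir 100 mg.

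**Shorter stays**
- Resident from Period 1 to Period 2, then home: the next scheduled test is Period 3 Day -3, at day 20 or later. Only Period 2 dosing falls in the gap.
- Home after Period 1, then resident from Period 2 to Period 3: the gap is at least 30 - 10 = 20 to 37 - 10 = 27 days and covers the Period 2 and Period 3 doses, starting from a fresh negative test.

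**When the Appendix 6 trigger would act.** Assumption, not in the documents: conception 0 to 5 days before the Period 1 Day -3 test, and menses due 12 to 16 days after conception. The missed cycle then falls between 12 - 5 = 7 and 16 - 0 = 16 days after that test. Against the table:
- the Period 2 run-in (day 11) and dose (day 13) lie inside the 7 to 16 day range, so the trigger can come before or after Period 2 dosing at the minimum spacing;
- the Period 3 run-in (day 21) and dose (day 23) lie beyond it, so a working trigger comes before Period 3.

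**What the waived tests would add.** Assume, again from outside the documents, that a pregnancy becomes detectable D days after conception, with D from 8 to 14. A conception x days before the Period 1 test is missed there if x < D, and is detectable at the Period 2 Day -3 test if x + 10 >= D. With D = 8 that holds for every x. With D = 14 it fails for x = 0 to 3. At the Period 3 Day -3 test, x + 20 is at least 20, above 14, so all are detectable. Restoring the tests therefore narrows the Period 2 gap without always closing it, and closes the Period 3 gap over the assumed range.

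**Footnote 1.** Read literally, a follow-up after Period 2 falls 13 + 7 = 20 to 13 + 14 = 27 days after the first test. It then need not follow the Period 3 dose at all. The timing of the last scheduled test is unclear until this is reconciled.

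**The case against.** The strongest reply is that footnote 2 does not stand alone. Appendix 6 makes a test mandatory after a missed cycle or on suspicion. Entry requires a recent confirmed period and a negative sensitive test. Section 6.1 asks for two contraceptive methods including a barrier, with an exemption for abstinence or same-sex partners. The waiver has a rationale, since a woman who goes home has a new opportunity to conceive and a confined woman does not. Section 5.1 describes admission and discharge period by period, and the review of Part 1A data before Part 1B makes an unbroken three-period stay less likely. The protocol also accepts a gap elsewhere: in Part 2 the scheduled tests are at Day -1 and follow-up, which is 1 + 10 + 7 = 18 to 1 + 10 + 14 = 25 days, across 11 daily doses.

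Most of this stands. It rules out two stronger conclusions that a reader might draw. One is that a missed early pregnancy would certainly go undetected through both later periods. That needs a continuous stay and failure of a mandatory trigger, for instance through irregular cycles or bleeding taken for menses. The other is that a possible interaction with hormonal contraceptives makes this scenario worse. The conception in question precedes any study drug, and Section 6.1 already deals with the interaction by requiring other methods.

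What the reply does not remove is that Table 2 neither refers to the Appendix 6 trigger nor schedules a menstrual history, and the protocol does not say how a missed cycle is to be identified. On the assumptions above, the trigger can also come after Period 2 dosing. Confinement answers the risk of a new conception, not of one just before admission. Part 2 differs because it is a single continuous course, whereas Part 1 restarts treatment at points where a test is already in the schedule and is then waived.

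**Conclusion.** The point holds as a modest safety and consistency issue. For women resident across Part 1 periods, footnote 2 and its SAP copy leave only event-triggered or discretionary testing from the Period 1 Day -3 test until follow-up. That is at least 30 to 37 days if the stay covers all three periods, and less otherwise. A conception too recent for the first test may go unnoticed through Period 2 dosing; reaching Period 3 unnoticed also needs the trigger to fail. The documents do not support saying that resident women are dosed with no check at all, because the Appendix 6 tests apply to them.

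The absolute risk is low, and the documents do not say how many women, if any, would be resident across periods. The day counts rest on the stated minimum intervals. The placement of the missed cycle and the reach of the restored tests rest on assumed ranges. No PK or statistical result is affected.

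**What to change.** In Table 2 footnote 2 and SAP Section 14.2.1, delete the four words that extend the residency waiver to the pregnancy test, so that it covers only the drug, alcohol and cotinine screen. The Day -3 test already entered for Periods 1 to 3 then applies to every woman in Part 1, in line with inclusion criterion 6 and Appendix 6. At the same time, reconcile footnote 1 with the three-period design and with follow-up 7 to 14 days after the last dose. No new dosing rule is proposed.

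The cost is one footnote edit in each document and at most two extra pregnancy tests per resident woman. The PK sampling times and the analysis are unchanged.

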3. INTRODUCTION

3.1. Study Rationale

This will be a two-part study design that will confirm the acceptability/selection of a tablet formulation for future clinical development of GSK2838232.

Part 1 is a relative bioavailability study that will assess single RTV-boosted doses of a novel tablet formulation given with food (normal, approximately 30% fat) against the reference capsule formulation also given with food (Part 1A) and then will assess the impact of fasted conditions on the tablet performance (Part 1B).

Part 2 is a study of non-boosted GSK2838232, given as once-daily tablet doses for 11 days in a separate cohort of participants, assuming the tablet performance is considered acceptable from Part 1A. The dose of GSK2838232 used in Part 2 will be confirmed after Part 1A but is likely to be, and will not exceed, 500 mg QD as tablets.

3.2. Background

Human immunodeficiency virus (HIV) infection affects approximately 37 million people worldwide [UNAIDS Fact Sheet, 2015]. While antiretroviral (ARV) therapy has been tremendously successful over the past 20 years in reducing morbidity and mortality, there continues to be a medical need given viral resistance to existing drug classes and acute and chronic drug toxicities. New drug classes targeting novel viral replication mechanisms would overcome HIV resistance to existing ARV drugs and may improve long-term safety by replacing older agents with known safety liabilities.

Maturation inhibitors represent a new class of compound for the treatment of HIV infection, distinct from viral entry, protease, reverse transcriptase or integrase inhibitors [Qian, 2009]. GSK2838232 is a maturation inhibitor being developed for the treatment of human HIV-1.

An extensive preclinical package of work has been completed, including biology/ virology, safety assessment (toxicology), and preclinical PK studies. GSK2838232 has also been administered to 124 healthy non-HIV-infected human participants in four clinical studies completed so far across a number of single and repeated dose designs, utilizing early clinical formulations. The PK, safety, and tolerability profile obtained so far supports continued clinical development of GSK2838232, and there is an ongoing study in HIV-infected patients that was initiated in the United States (US) in 1Q2017. There is a need to transition to a more suitable tablet formulation, which is one of the major objectives of this study.

3.2.1. Pharmacokinetic Summary

The original formulation used in the first three studies with GSK2838232 (HMI116787, 200207, and 200912) was Spray Dried Dispersion (SDD). Data from Study 200912 demonstrated that a change to the active pharmaceutical ingredient (API) formulation of

GSK2838232 was feasible for future clinical studies. Study 204953 utilized micronized API powder in a bottle as well as in a capsule.

- GSK2838232 SDD did not overall demonstrate significant escalation in exposure from an increase in dose from 100 mg to 200 mg in a cross-study comparison. The API powder in bottle (PiB) formulation showed a proportional increase in AUC and Cmax for a 2-fold dose escalation from 100 mg to 200 mg.
- The observed tmax of the API form was significantly increased over the SDD formulation (the API formulation also increased tlag relative to SDD).
- The bioavailability of the GSK2838232 API formulation was on average 30 to 50% of the bioavailability of SDD formulation, but there was a large observed range of relative intra-subject exposures (11 to 150%).
- Both 10 mg SDD and 20 mg API showed a 10-fold or greater increase in AUC with steady-state RTV (100 mg QD for 10 days) with a smaller (≤ 4-fold) increase in observed Cmax. The t½ of GSK2838232 increased from 15 to 18 hours to 34 to 42 hours in the presence of steady-state RTV, regardless of formulation.
- After single doses of 50 mg to 250 mg GSK2838232 with RTV, increases in maximum observed concentration (Cmax) and area under the concentration-time curve from time zero (pre-dose) extrapolated to infinite time (AUC[0-∞]) values were broadly proportional to the increase in dose. On Day 11 after repeated daily 20 mg to 200 mg doses of GSK2838232 with RTV, increases in Cmax and area under the curve (Area under the plasma drug concentration-time curve from pre-dose to the end of the dosing interval at steady state) (AUC[0-τ]) values appeared to be proportional to the increase in dose with the PiB and capsule formulations.
- The relative bioavailability of the micronized API powder blend in capsules with RTV was approximately 45% to 60% higher than the bioavailability of the micronized API administered as oral suspension from PiB with RTV.
- Co-administration of the micronized API powder blend in capsules with RTV and a normal fat meal resulted in an approximately 60% increase in geometric mean Cmax and AUC(0-∞) values compared to the fasted state with RTV.

Variability remains fairly constant across formulations and boosted versus unboosted at around 30% to 40% (moderate-high).

Full details of non-clinical and clinical data may be found in the current Investigator's Brochure (IB) [GlaxoSmithKline (GSK) Document Number 2012N151889 03].

